9.1 Disposition of Subjects

The number of eligible subjects and number of subject reached study completion will be counted and summarized. The denominator of percentage of number of eligible subjects will be the number of subject screened. The denominator of percentage of number of subject complete the study will be the number of eligible subjects. The summary of reason for early termination will be provided as well. The denominator of the reason will be the number of subjects not complete the study.

9.2 Protocol Violations and Deviations

This is an observational study. Investigator could follow their practice and judgment. No protocol violation and deviation will be defined.

9.3 Demographic and Baseline Characteristics

The following demographics and baseline characteristics will be collected at visit 1: age, gender, race, education level, environmental/ occupation exposures, smoking status, height, weight, IPF characteristics, and comorbidity. Age will be calculated as $(\text{date of informed consent} - \text{date of birth})/365.25$. Age, weight, and height will be summarized as continuous. While the other demographics will be presented as categorical.

IPF characteristics including the duration of IPF from initial diagnosis to the date of informed consent, HRCT pattern, UIP pattern, surgical lung biopsy, and multidisciplinary term diagnosis. duration of IPF will be summarized as continuous and the other IPF characteristics will be summarized as category.

9.4 Current Concomitant Medications

Concomitant medications will be collected at visit 1. The concomitant medications will be grouped per the indications into DM, Hypertension, Hyperlipidemia, CVD/cerebral artery occlusion, Respiratory, and other medication. The number of medication and number of subjects with the medication will be presented by the group of medication.

10 DEFINITION AND DETERMINATION OF ANALYSIS VARIABLES

10.1 Treatment Exposure and Compliance

Treatment exposure will be counted as total days of using anti-fibrotic drugs during the study. The summary of treatment exposure will be presented by the treatment of nintedaninb and pirfenidone. If the subjects ongoing use anti-fibrotic drug in the end of study, the duration will be counted to the last known date subject took anti-fibrotic drug.

Due to this study is an observational study. Investigator will give prescription per the judgement of medical practice. Hence, treatment compliance is not applicable and will not be computed.

10.2 Primary Endpoint(s)

- Annual percentage of decline from baseline in FVC

Values of FVC (% pred.) will be used for this endpoint. The FVC(% pred.) collected at visit 1 will be served as baseline.

- Annual decline from baseline in DLco

Values of DLco (% pred.) will be used for this endpoint. The DLco (% pred.) collected at visit 1 will be served as baseline.

- Annual decline from baseline in resting and exercise SpO₂

Values of SpO₂ (%) will be used for this endpoint. The SpO₂ (%) collected at visit 1 will be served as baseline.

- Annual percentage of decline from baseline in TLC

Values of TLC (% pred.) will be used for this endpoint. The TLC (% pred.) collected at visit 1 will be served as baseline.

- Annual percentage of decline from baseline in IC

Values of IC (% pred.) will be used for this endpoint. The IC (% pred.) collected at visit 1 will be served as baseline.

Annual percentage of decline and annual decline from baseline will be calculated as

$$\text{Annual decline} = \frac{\text{Value}_{\text{follow-up}} - \text{Value}_{\text{baseline}}}{\text{Days of follow-up}} \times 365.25$$

In addition to the annual decline, the mean value and mean change from baseline will also be presented for the lung functions. Descriptive statistics including Number, Mean±SD, Median, Range and 95% C.I. of mean value and mean change from baseline at each visit will be calculated and listed.

10.3 Secondary Endpoints

- Time to first acute exacerbation of IPF after enrolment

Time to first acute exacerbation starts from the date of informed consent to the date of first acute exacerbation recorded on the CRF. Subject with exacerbation free at the time of the last contact will be censored. The time of censored is from the date of consent to the last valid date of last known date subject took anti-fibrotic drugs, date of last contact, and last visit date.

- Annual change from baseline in SGRQ

Descriptive statistics including Number, Mean±SD, Median, Range and 95% C.I. will be presented. Annual change from baseline in SGRQ will be calculated as

$$\text{Annual change from baseline} = \frac{\text{SGRQ}_{\text{follow-up}} - \text{SGRQ}_{\text{baseline}}}{\text{Days of follow-up}} \times 365.25$$

In addition to the annual change from baseline, the mean value and mean change from baseline will also be calculated.

- Annual change from baseline in CAT

Descriptive statistics including Number, Mean±SD, Median, Range and 95% C.I. will be presented. Annual change from baseline in CAT will be calculated as

$$\text{Annual change from baseline} = \frac{\text{CAT}_{\text{follow-up}} - \text{CAT}_{\text{baseline}}}{\text{Days of follow-up}} \times 365.25$$

In addition to the annual change from baseline, the mean value and mean change from baseline will also be calculated.

- Annual change from baseline in 6MWT

Descriptive statistics including Number, Mean±SD, Median, Range and 95% C.I. will be presented. Annual change from baseline in 6MWT will be calculated as

$$\text{Annual change from baseline} = \frac{6\text{MWT}_{\text{follow-up}} - 6\text{MWT}_{\text{baseline}}}{\text{Days of follow-up}} \times 365.25$$

In addition to the annual change from baseline, the mean value and mean change from baseline will also be calculated.

- Mortality (with cause of death) and time to death

Time to death is calculated from the date of consent to the date of death from any cause. Subjects with no documented death will be censored. The time of censored is from the date of consent to the last valid date of last known date subject took anti-fibrotic drugs, date of last contact, and last visit date.

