During the following observational period until the end of study observation (Week 100), data collection will be performed every 12 weeks (3 months) with an allowed window of ± 1 month. The following assessments will be documented:

- Record of IPF symptoms
- Record of current anti-fibrotic drugs used for IPF (i.e., nintedanib and pirfenidone) and reasons and date for dose change or discontinuation

Non-interventional Study Protocol
BI Study Number 1199-0303

c16462309-02

Proprietary confidential information © 2017 Boehringer Ingelheim International GmbH or one or more of its affiliated companies

- Collect spirometry results
- Collect 6MWT results (only at Week 52 and 100)
- Collect St. George's Respiratory Questionnaire (SGRQ) results
- Collect COPD Assessment Test (CAT) results
- Collect Berlin questionnaire results for patients with comorbidity of obstructive sleep apnea (only at Week 28, 52, 76, and 100)
- Collect echocardiography results for patients with comorbidity of PH (only at Week 28, 52, 76, and 100)
- Record of any acute exacerbations since the preceding visit
- Conduct safety reporting for OFEV[®] relevant ADR (serious, non-serious), fatal AEs, and pregnancies; and record them on corresponding ADR forms and CRF pages
- Collect data of serological tests (only at Week 16, 52, 76, and 100)
- Collect data of biomarker tests (only at Week 52 and 100)

Remark: Since this is a non-interventional, observational study, all the tests collected will be performed as judged appropriate by the treating physician, however for test marked as mandatory variables it will be at least assessed if the test has been performed and if yes the results of interest will be recorded. This study does not require additional tests or examinations to be performed.

Table 1 is the recommended data collection schedule that most likely mirrors the patterns of routine clinical care of most IPF patients. The sign “X” indicates when the data will be collected if available.

Table 1 Data Collection Schedule

Week [#] Visit	Baseline	Wk 4	Wk 16	Wk 28	Wk 40	Wk 52	Wk 64	Wk 76	Wk 88	Wk 100
	1	2	3	4	5	6	7	8	9	10
Variables			← 3-month interval →							
Allowed window		± 14 days	← ± 1 month →							
Informed consent	X									
Inclusion/exclusion	X									
Demographics ¹	X									
IPF characteristics (diagnosis) ^{*, 2}	X									
IPF symptoms ³	X	X	X	X	X	X	X	X	X	X
Smoking status	X									
Comorbidities	X									
- STOP-Bang Scoring Model ⁴	X ^{&}									

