9.3 VARIABLES

9.3.1 Exposures

Currently, 2 anti-fibrotic drugs, namely nintedanib and pirfenidone, have been approved for treating IPF patients. The use of nintedanib and pirfenidone will be according to the Summary of Product characteristics and physician's discretion. Prescription of nintedanib and pirfenidone will be collected and recorded on CRF during the observational period, including start/end date, dose, and the reason for dose adjustment or interruption.

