9.7.1 Main analysis

The analysis for primary and secondary outcomes, including results of spirometry tests, SGRQ, CAT, and 6MWT will be conducted on the basis of continuous variables, with number, mean (for annual change/decline from baseline, one mean annual change over the whole study period [0-2 years as maximum] will be presented), standard deviation, minimum, Q1 (lower quartile), median, Q2 (upper quartile), maximum value, and 95% confidence intervals included. Wilcoxon Signed Ranked test or t-test, whichever is applicable, will be used to test the change from baseline under a significant level of 0.05.

Time to first acute exacerbation and mortality will be analyzed by Kaplan-Meier estimates, with incidence and time to event included. Time to first acute exacerbation starts from the date of enrolment to the date of first acute exacerbation recorded on the CRF. Patients with exacerbation free at the time of the last contact will be censored. The time of event data will be analyzed using Kaplan-Meier curves. The median, range, and 95% CI for median time and will be reported. Time to death is calculated from the date of enrolment to the date of death from any cause. Patients with no documented death will be censored at the last time they were known to be alive at the time of the last contact. The time of event data (overall survival, censored at 100 weeks) will be analyzed by Kaplan-Meier survival method. The median, range and 95% CI for median survival time and survival curve will be reported.

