9 SUMMARY OF STUDY DATA

All the statistical analysis will be performed and categorized by the subgroup of with anti-fibrotic drug and no anti-fibrotic drug. The summary tables will be tabulated with columns of the two subgroups. The relevant population size will be annotated in the tables.

Continuous variables will be summarized by descriptive statistics: number of observations, mean, median, standard deviation, range, and 95% confidence interval. Frequency counts and percentages of observed levels will be reported for categorical variables. The denominator of percentages will be the number of subjects with valid assessment results. Subjects with missing data will not be included in the number of denominator.

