12 SUMMARY OF CHANGES TO THE PROTOCOL

The initial statistical analysis plan will follow the protocol design and no changes or differences will be planned in the initial statistical analysis plan.

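### SAP 10.3 lets an anti-fibrotic intake date, which only treated patients can have, carry exacerbation censoring past the last date status was known; any effect favours the treated column and is probably small

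*SAP*

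**What the plan says.** - **Protocol 9.7.1, exacerbation:** "Patients with exacerbation free at the time of the last contact will be censored". No drug date is mentioned.
- **Protocol 9.7.1, death:** "Patients with no documented death will be censored at the last time they were known to be alive at the time of the last contact". Overall survival is also censored at 100 weeks.
- **SAP 10.3, both outcomes:** the censoring time runs from consent to "the last valid date of last known date subject took anti-fibrotic drugs, date of last contact, and last visit date". For exacerbation, the preceding sentence is "Subject with exacerbation free at the time of the last contact will be censored". No 100-week cap is stated.
- **SAP 8.4 and 9:** a patient with no anti-fibrotic record during observation is in the untreated group, and a patient with at least one is in the treated group. Then: "All the statistical analysis will be performed and categorized by the subgroup of with anti-fibrotic drug and no anti-fibrotic drug".
- **Protocol 9.2.3, follow-up visits:** "Record of any acute exacerbations since the preceding visit". Exacerbations are captured by looking back at each visit.
- **Protocol 9.3.1:** "Prescription of nintedanib and pirfenidone will be collected and recorded on CRF during the observational period, including start/end date".
- **SAP 12:** "no changes or differences will be planned in the initial statistical analysis plan".

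**The concern.** A patient should stay in the Kaplan-Meier risk set only while an event would be seen if it happened. For exacerbation, that period ends at the last visit or contact at which status was asked about or recorded. SAP 10.3 allows a later end date, but only for patients who have taken an anti-fibrotic drug.

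The variable that defines the two columns therefore also feeds the censoring date of one of them. If the drug date falls after the last contact and last visit, the treated patient adds to the denominators without being able, in the ordinary course, to add to the numerators. The treated curve then sits slightly too high for a reason unrelated to the disease or the drug. SAP 12 does not list the added date as a departure from the protocol, so a reader of the report would not be alerted to it.

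**Working it through.** **1. No plan figure to reproduce.** The sample size of about 100 rests on recruitment time and patient pool (Protocol 9.5, SAP 7.4). Neither document gives an exacerbation rate, a drop-out rate or an event count. The rates below are assumptions.

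**2. The two rules compared.**
- Protocol: censor at last contact.
- SAP: censor at max(last drug date, last contact, last visit).
- Gain per patient due to the drug date = max(0, last drug date − later of last contact and last visit).

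Example with last contact and last visit on day 400:

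| Last drug date | SAP censoring | Gain |
|---|---|---|
| day 390 | day 400 | 0 |
| day 400 | day 400 | 0 |
| day 428 | day 428 | 28 days |
| day 484 | day 484 | 84 days |

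**3. Direction.** The gain is never negative. By SAP 8.4 it is always zero in the untreated column, and a drug date before enrolment cannot extend follow-up. Any effect therefore lowers apparent exacerbation incidence in the treated column only.

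**4. Size.** Assume a constant exacerbation hazard h and early-loss hazard c (per year), a share q of early leavers with a late drug date, and an extension of E years with no recordable event. Once t exceeds E, the number wrongly kept at risk, relative to those truly observed, is

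R = q × c/(h+c) × (exp((h+c)E) − 1),

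and the apparent hazard is h/(1+R).

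Worked case: h = 0.10, c = 0.30, q = 1, E = 84/365.25 = 0.230 (one 12-week visit interval).
- exp(0.40 × 0.230) − 1 = 0.0964
- R = 0.75 × 0.0964 = 0.0723
- Apparent hazard = 0.10/1.0723 = 0.0933

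Integrating to day 700 (week 100), with the smaller R during the first E years, gives:

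| h | c | q | E (days) | Incidence, last contact rule | Incidence, SAP rule | Difference (points) |
|---|---|---|---|---|---|---|
| any | any | any | 0 | – | – | 0 |
| 0.05 | 0.10 | 0.25 | 28 | 9.14% | 9.12% | 0.02 |
| 0.10 | 0.10 | 0.25 | 28 | 17.44% | 17.41% | 0.03 |
| 0.10 | 0.30 | 0.50 | 84 | 17.44% | 16.92% | 0.52 |
| 0.10 | 0.30 | 1 | 84 | 17.44% | 16.43% | 1.01 |
| 0.20 | 0.30 | 1 | 84 | 31.84% | 30.14% | 1.7 |

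**5. A harsher case.** Take h = 0.25 and c = 0.35, the protocol's Table 1 visit weeks, and censoring at the last attended visit. Simulated exacerbation-free survival at 1.9 years moves from 0.622 to 0.646, about 2.4 points, if every event-free treated patient is extended by 12 weeks. If a quarter are extended, it moves from 0.622 to 0.628.

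**6. Scale.** With an assumed 50 patients per column and survival of 0.62, the standard error without censoring is √(0.62 × 0.38/50) = 0.069, or about 7 points.

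**The case against.** **The gain is not automatic.** A reader might infer that every treated patient gains follow-up, because a refill issued at the last visit has an end date weeks later. The documents do not support this. SAP 10.3 refers to the last known date on which the drug was taken, not to the end of a prescription, and SAP 10.1 uses the same term for patients still on treatment. A known intake date is normally learned at a contact, and then the gain is zero. This objection stands. What remains is that the CRF holds prescription start and end dates, neither document says which field supplies the intake date, and the date of last contact is undefined. The rule therefore permits the extension without showing how often it occurs.

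**Late exacerbations are not impossible to record.** Protocol 9.4 lists hospital discharge files and electronic records as sources. Protocol 9.3.4 asks for an end-of-study visit at discontinuation and a further assessment if possible. It is correct to say only that status after the last visit or contact would not normally be ascertained. Protocol 9.7.4 adds that no further efforts will be made to obtain information.

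**The same criticism might be extended to time to death.** It largely fails there. A documented intake date shows that the patient was alive that day, which fits the protocol's rule. Only a supply end date would be open to objection, and the SAP does not name one.

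**A larger effect might be inferred from person-time rates.** With the rates of the harsher case, the treated event rate falls from 0.25 to 0.217 per year, about 13%. That requires extending every event-free treated patient by 12 weeks, completers included, past week 100. Capped at week 100, the rate is 0.230 (8% low). If a quarter are extended and the cap is kept, it is 0.245 (2% low). SAP 11.4 lists Kaplan-Meier curves and quartiles, not a person-time rate.

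**Nor do the documents show a rule designed to favour the sponsor's drug.** The treated column pools nintedanib with pirfenidone, no between-group survival test is planned, and SAP 8.7 says the study does not aim to show treatment differences.

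**Conclusion.** The point holds for time to first acute exacerbation as a flaw in a stated rule. The drug date either changes nothing or lengthens treated follow-up beyond the date at which the SAP itself judges status. It can do so in one column only, and Protocol 9.7.1 contains no such date.

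The effect is conditional and probably small: about 0 to 2.5 percentage points of Kaplan-Meier incidence near week 100. This rests on assumed exacerbation hazards of 0.05 to 0.25 per year, early loss of 0.10 to 0.35 per year, and extensions of up to 12 weeks. It also rests on reading the SAP wording as the latest of the three dates. If something else is meant, the rule is ambiguous and still depends on a date that one group lacks. The upper end is well inside the sampling error of a column of about 50 patients, and it affects descriptive side-by-side curves only.

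The case for correcting it is that the direction is fixed, the departure is undeclared and the change costs almost nothing.

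**What to change.** - **Exacerbation (SAP 10.3):** remove the drug date. Censor both columns at the last visit or contact at which exacerbation status was recorded, capped at the end of the observation period. Define the date of last contact.
- **Death (SAP 10.3):** keep the protocol's rule of the last date known to be alive. Count a drug date only if it is documented actual intake, not a prescription or supply end date. Apply the 100-week cap stated in Protocol 9.7.1.
- **SAP 12:** list any departure from Protocol 9.7.1 that remains.

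The cost is a wording change and a small edit to the derivation code. Some treated patients would have slightly shorter follow-up for exacerbation.

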10.4 Safety Endpoints

- Frequency of adverse events and serious adverse events.

All adverse events will be summarized with the coding term, severity, and relationship to nintedanib by frequency tables with the counts and percentage.

11 STATISTICAL METHODS

11.1 Primary Hypothesis

The hypothesis for the analysis of the primary outcome is

$$H_0 : \text{Annual Decline} = 0 \text{ vs. } H_a : \text{Annual Decline} \neq 0$$

11.2 Test of Assumptions

The primary outcomes will be tested by paired t-test. The assumption of normality will be tested by Shapiro-Wilk test. Wilcoxon sign rank test will be used if the assumption of normally distributed is violated.

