11.3 Primary Endpoint Analysis

Annual declines will be summarized with descriptive statistics including Number, Mean \pm SD, Median, Range and 95% C.I. Annual decline will be tested by paired t-test to show if significant change. The Wilcoxon sign rank test will be used if the normally distributed assumption is violated. The test is two sided and the significant level is set as 0.05. The sas procedure used for the tests is listed as follow.

Statistical Test	SAS procedures and option
Shapiro-Wilk test	PROC UNIVARIATE NORMALTEST
T-test	PROC UNIVARIATE MU0=0 ALPHA=0.05
Wilcoxon sign rank test	PROC UNIVARIATE MU0=0 ALPHA=0.025

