11.6 Interpretation and Conclusion

The change from baseline endpoints will be assessed by two-sided paired T-test or Wilcoxon signed rank test under significance level 0.05. Once the p-value is lower than the significance level, the significant change could be claimed.

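### A Shapiro-Wilk switch picks the test while the planned summary stays a mean with its interval, so a claimed change can contradict the reported 95% CI

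*SAP*

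**What the plan says.** SAP 11.1 introduces its null with "The hypothesis for the analysis of the primary outcome is" and sets annual decline equal to zero. It does not say whether that is a mean, a median or a pseudo-median.

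SAP 11.2 adds the gate: "The assumption of normality will be tested by Shapiro-Wilk test", and "Wilcoxon sign rank test will be used if the assumption of normally distributed is violated". No cut-off is given for calling normality violated. SAP 11.3 makes the t-test the default ("Annual decline will be tested by paired t-test to show if significant change") and fixes the level: "The test is two sided and the significant level is set as 0.05". SAP 11.4 applies the same procedure to SGRQ, CAT and 6MWT. SAP section 9 runs all analyses in two columns, with and without anti-fibrotic drugs, so the gate operates separately in each.

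The summary is the same whichever test is chosen. SAP 11.3 begins "Annual declines will be summarized with descriptive statistics including Number" and continues with mean and SD, median, range and a 95% CI. SAP 10.2 ties the CI to the mean for the by-visit summaries. For annual decline the parameter is not named, but Protocol 9.7.1 says "one mean annual change over the whole study period [0-2 years as maximum] will be presented". No interval matched to the signed-rank test is planned.

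SAP 11.6 gives the claim rule: "Once the p-value is lower than the significance level, the significant change could be claimed".

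**The concern.** The t-test and the t-based CI of the mean are the same calculation, so they cannot disagree. The signed-rank test addresses a different quantity unless the distribution is symmetric. Once the gate selects it, the p-value behind the claim and the printed interval come from different analyses. A report could then claim a significant change beside a 95% CI of the mean that includes zero, or make no claim beside a CI that excludes it.

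If skew is what trips Shapiro-Wilk, the fallback loses the symmetry it needs to speak to the mean. And because the data choose the test, different endpoints, or the two drug columns of one endpoint, can be judged on different quantities within one table.

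**Working it through.** The documents contain no power or error-rate figure to reproduce: N of about 100 is a feasibility number (SAP 7.4). The check is therefore by simulation. Taken from the documents: n = 100, two-sided 0.05, the switch rule, the Table 1 visit times and the SAP 10.2 formula. Assumed: a Shapiro-Wilk cut-off of 0.05 and every distribution shape.

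**Baseline.** With normal data and a true mean of 0, the rule rejects in 4.9% to 5.8% of runs. Test and CI of the mean disagree in 0.2% to 0.6%. The switch is harmless if the rates are close to normal.

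**Case A: skewed data, mean as target.** Mean-centred gamma samples, true mean 0, n = 100:

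| Skewness (assumed) | Switch rule rejects | t-test rejects |
|---|---|---|
| 1 | 14% | 5-6% |
| 1.5 | 24% | 5-6% |
| 2 | 37% | 5-6% |

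Repeat runs moved these by one or two points (13% at skewness 1, 39% at skewness 2). At n = 50 the rule rejects about 9%, 15% and 22% to 24%. The error also runs the other way: with a true mean of -0.3 SD and skewness -1, the rule detects 60.8% against 86.8% for the t-test, and the two disagree in 26.0% of runs.

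One simulated sample of 100 shows the contradiction: mean 0.40, 95% CI -1.31 to 2.11, t-test p = 0.64, Shapiro-Wilk p < 0.001, signed-rank p = 0.007. Under SAP 11.6 a change could be claimed.

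**Case B: the SAP's own annualisation.** The rate is change / days × 365.25. The multiplier is 365.25/28 = 13.0 at Week 4 and 365.25/700 = 0.52 at Week 100, a 25-fold range. With follow-up T in years and independent measurement error of SD σ at each of the two points, the variance of one patient's rate is (slope SD)² + 2σ²/T². Taking slope SD 6 and σ = 5:

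- Week 4 (T = 0.0767): 36 + 50/0.00588 ≈ 8,544, SD about 92.
- Six months (T = 0.5): 36 + 50/0.25 = 236, SD about 15.
- Week 100 (T = 1.916): 36 + 50/3.673 = 49.6, SD about 7.

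Mixing such variances around one mean gives heavy but symmetric tails, so Shapiro-Wilk fires without skew.

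The simulation used a true decline of 5 points/year, the last value as follow-up, and exponential survival with the medians of 0.9 and 3 years cited in Protocol section 7. Shapiro-Wilk rejected in 97% to 100% of studies.

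| Median survival | Slope SD, σ | Signed-rank detects | t-test detects |
|---|---|---|---|
| 0.9 years | 6, 3 | 98% | 55% |
| 0.9 years | 8, 5 | 80% | 27% |
| 3 years | 6, 3 | 100% | 90% |
| 3 years | 8, 5 | 99% | 62% |

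Test and CI of the mean disagreed in about 10% to 54% of studies. Practically all of these were a significant signed-rank result with zero inside the CI, while the true decline was not zero. With a true decline of 0, the rule rejected about 5%. Requiring at least six months of follow-up cut disagreement to 0% to 0.5%.

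**Columns.** With the same skewness in both columns and an assumed 70/30 split, the gate sent the two columns to different tests in 36%, 54% and 21% of runs at skewness 0.5, 1 and 1.5. Only the column sizes differed.

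**The case against.** The strongest defence is Case B. In the only model built from this study's formula and visits, skew is near 0, the rule keeps its 5% level, and the signed-rank test finds real declines that the t-test misses. That stands. So does its corollary: the 10% to 54% disagreement comes mainly from annualising very short intervals, not from the switch itself.

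A reader might infer from Case A that the rule inflates false positives in this study. The documents do not support that. They give no skewness for any endpoint, and the null in SAP 11.1 does not name the mean. A reader might equally infer that a mean-based t-test should simply replace the switch. Case B shows that could cost much of the power.

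It can also be said that the protocol calls the study essentially descriptive, that Protocol 9.7.1 already allows either test, and that the median is printed too. These points carry less weight. SAP 8.7 disclaims hypothesis testing, but SAP 11.1 to 11.6 set out a hypothesis, a level and a claim rule. The protocol's permission does not require a pre-test. The median has no planned interval, and under skew the signed-rank test does not test the median either.

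**Conclusion.** The point holds as a mismatch between the test that permits a claim and the interval printed beside it. That the 95% CI for annual decline is the mean's is an inference from Protocol 9.7.1 and SAP 10.2; the SAP refers its table shells to separate mock-up tables.

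The size is conditional:

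- Near-normal rates: negligible.
- Skewness 1 to 2 with the mean as target: about 14% to 37% rejection of a true zero at n = 100, against 5%.
- Symmetric heavy tails from short follow-up: the level holds, but claim and interval disagree in about 10% to 54% of studies, falling below 1% with at least six months of follow-up.

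These figures rest on the assumed 0.05 cut-off, the assumed shapes, and the last value as follow-up, which SAP 10.2 does not specify. They leave out the visit-mean imputation of SAP 8.5, which would change the distribution of the lung-function endpoints. The issue deserves correction before database lock, but it does not show that the switch produces false claims in this study.

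**What to change.** In SAP 11.1 to 11.4 and 11.6:

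- Name the parameter in the null hypothesis.
- Replace the Shapiro-Wilk switch with one pre-specified test per endpoint, the same in both drug columns.
- Take the p-value and the 95% CI behind any claim from the same analysis: either the t-test with the mean and its CI, or the signed-rank test with the Hodges-Lehmann estimate and its CI. Show the other as supportive.

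Either pairing puts p-value and interval on the same parameter. Settle the choice together with the definition of the follow-up value in SAP 10.2. If very short intervals are still annualised, a mean-based primary test can lose substantial power (98% to 55% in one scenario above). If they are not, the two tests performed almost alike in the symmetric model.

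At minimum, keep the present rule but state its cut-off, and report the Hodges-Lehmann estimate with its CI wherever the signed-rank test is used.

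The cost is SAP wording and a little programming. No new data are needed. Protocol 9.7.1 already allows either test, and Protocol 9.7 asks for an amendment only when a principal feature of the objective changes.
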